7 DISCONTINUATION OF STUDY INTERVENTION AND PARTICIPANT DISCONTINUATION/WITHDRAWAL

7.1 Discontinuation of Study Intervention

It may be necessary for a participant to permanently discontinue (definitive discontinuation) study intervention. If study intervention is permanently discontinued, the participant will remain in the study to be evaluated for safety and efficacy during the 30-day follow-up period (Section 8.2.1), or until documented disease progression during the long term follow-up period (Section 8.2.2). See the SoA for data to be collected at the time of discontinuation of study intervention and follow-up and for any further evaluations that need to be completed.

Note that discontinuation from study intervention is NOT the same as a withdrawal from the study.

The participant should continue attending subsequent study visits and data collection should continue according to the study protocol. If the participant does not agree to continue in-person study visits, a modified follow-up must be arranged to ensure the collection of endpoints and safety information. This could be a telephone contact with the participant for the follow-up visit, a contact with a relative or treating physician, or information from medical records. The approach taken should be recorded in the medical records. A participant who agrees to modified follow-up is not considered to have withdrawn consent or to have withdrawn from the study.

Participants may be discontinued from study intervention in the following situations:

- Objective disease progression assessed by investigator
- Adverse event as defined in Section 8.3
- Participant or investigator decision. The participant is at any time free to discontinue treatment, without prejudice to further treatment
- Pregnancy (See Section 8.3.10)

- Non-compliance with the CSP (investigator or participant)
- Participant incorrectly initiated on study treatment
 - When the reason does not impact safety, the Study Physician together with the investigator will consider the risk/benefit to the participant of stopping treatment.
 - The Study Physician is responsible for ensuring all such contacts are appropriately documented.
- Unexpected, significant, or unacceptable risk to the participants enrolled in the study.
- Sponsor termination of study for reasons including but not limited to unfavourable risk/benefit or change in drug development plan.

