8 STUDY ASSESSMENTS AND PROCEDURES

- Study procedures and their timing are summarised in the SoA for the relevant module. Protocol waivers or exemptions are not allowed.
- Immediate safety concerns should be discussed with the sponsor immediately upon occurrence or awareness to determine if the participant should continue or discontinue study intervention.
- Adherence to the study design requirements, including those specified in the SoA, is essential and required for study conduct.
- All screening evaluations must be completed and reviewed to confirm that potential participants meet all eligibility criteria. The investigator will maintain a screening log to record details of all participants screened and to confirm eligibility or record reasons for screening failure, as applicable.
- Procedures conducted as part of the participant's routine clinical management (eg, blood count) and obtained before signing of the ICF may be utilised for screening or baseline purposes provided the procedures met the protocol-specified criteria and were performed within the time frame defined in the SoA.
- The maximum amount of blood collected from each participant over the duration of the study, including any extra assessments that may be required, is not anticipated to exceed 436.5 mL in Cycle 1 (cycle duration of 5 weeks) and 124 mL in each subsequent cycle (cycle duration of 3 weeks). Repeat or unscheduled samples may be taken for safety reasons or for technical issues with the samples.
- All efficacy assessments should continue until progression, including when a participant's study treatment has been stopped.

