8.2 Safety Assessments

Planned time points for all safety assessments are provided in the relevant module.

8.2.1 30-Day Follow-up Visit

A follow-up visit will be performed 30 (\pm 7) days from the time that all study intervention is permanently discontinued (see the SoA for the relevant module). Tumour assessments (including PET-CT) will be repeated at this visit if they have not been performed within 9 weeks if the participant discontinued before Week 26, or 12 weeks if the participant discontinued after Week 26.

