8.2.2 Long-term Follow-up Visit

Participants who discontinue all study intervention before documented disease progression will be followed according to standard of care until documented disease progression. Disease progression or start of new anticancer therapy will be captured in the eCRF. During this period, only information on any SAEs considered related to IP or study procedures will be collected. If a participant is unable to attend site for this visit, the LTFU may be performed via phone call. LTFU visits will cease at disease progression. The long-term follow up will not apply to participants who withdraw consent or are lost to follow-up.

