Serum immunoglobulins (IgA, IgM, IgG)	X		Day 1 of Cycles 3, 6 and 9 (pre-dose)			Cycle 13 (± 7 days) and every 6 months thereafter		X		10.8.2.6
Concomitant medication	X	X	X	X	X	X		X	X	5.2, 6.5
Adverse event evaluation		X	X	X	X	X		X	X	8.3
AZD4573 plasma PK		Refer to Section 10.8.6 for schedule								10.8.6
CCI [REDACTED]		X								10.8.6
Pharmacodynamic samples (blood) for AZD4573		Weeks 1 to 3								10.8.7
CCI [REDACTED]	X	Weeks 1 to 3	If elevated liver chemistry tests/bilirubin							10.8.9.3
Exploratory analyses samples	X	Refer to Section 10.8.8 for schedule								10.8.8

Table 9 Schedule of Activities: Module 1 (AZD4573 Monotherapy)

Procedure	Screening ^a	Cycle 1, Weeks 1-5 (includes intra- participant Dose ramp-up)	Cycle 2 to 12 (Cycle = 21 Days)			Cycles 13+ (Cycle = 21 days)	Disease Assessment	30-Day FU ^e	LTFU	Details in Section
		Cycle 1 Weeks 1-5, Day 1 Visits	Days			Day				
			1	8	15	1				
			(± 2 Days)	(± 2 Days)		(± 7 Days)	(± 7 Days)	(± 7 Days)		
Genomics Initiative sample (optional)		X								8.7
Bone marrow biopsy & aspirate (PTCL only) ^d	X						As clinically indicated and to confirm CR			10.8.9.1.1
Fresh or archival tumour tissue sample	X									10.8.9.1.2
Additional tumour biopsy sample (optional)							At disease progression	(X)		10.8.9.1.2
Disease assessments/radiologic scans	X		After Cycle 2 (+/- 1 week), then Q9W until W26 (Cycle 8, Week 3), then Q12W (+/- 1 week)					X		10.8.1
AZD4573 (IV; once weekly) ^c		X	X	X	X	X				10.6
Disease progression follow-up (SoC)									X	8.2.2

Table 9 Schedule of Activities: Module 1 (AZD4573 Monotherapy)

Procedure	Screening ^a	Cycle 1, Weeks 1-5 (includes intra- participant Dose ramp-up)	Cycle 2 to 12 (Cycle = 21 Days)			Cycles 13+ (Cycle = 21 days)	Disease Assessment	30-Day FU ^e	LTFU	Details in Section
		Cycle 1 Weeks 1-5, Day 1 Visits	Days		Day					
			1	8	15	1				
		(± 2 Days)	(± 2 Days)		(± 7 Days)	(± 7 Days)	(± 7 Days)	(± 7 Days)		
Survival FU ^e									X	8.2.3

^a Screening tests should be performed within 30 days before the first administration of study drug, unless otherwise indicated.

^b Informed consent must be obtained ≤ 30 days before first dose of study drug and must be obtained before any protocol-defined screening tests are done.

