10.8.1.2 Disease Assessment Schedule

Baseline tumour assessments will be performed using radiologic imaging by CT with contrast and PET-CT during the screening period. CT scans with contrast will cover neck, chest, abdomen, pelvis and any other disease sites; PET scans will cover the whole body from base of skull to mid-thigh.

Radiologic scans (ie, contrast CT) and PET scans will be performed as specified in [Table 15](#)

below, and thereafter to confirm CR or as clinically indicated. Unscheduled radiologic scans may be performed at investigator discretion if deemed clinically indicated.

Table 15 Radiologic Scans and PET Scans for Tumour Assessments

Timepoints		Required radiologic scans ^a	
Screening		Contrast CT	PET
During study ^b	After 8 weeks (~2 cycles)	Contrast CT	PET
	After 17 weeks (~5 cycles)	Contrast CT	
	After 26 weeks (~8 cycles)	Contrast CT	PET
	After 38 weeks (~12 cycles)	Contrast CT	
	After 50 weeks (~16 cycles)	Contrast CT	PET
	After 62 weeks (~20 cycles)	Contrast CT	
	After 74 weeks (~24 cycles)	Contrast CT	PET
	After 86 weeks (~28 cycles)	Contrast CT	
	After 98 weeks (~32 cycles)	Contrast CT	PET
	Every 12 weeks (~4 cycles) thereafter until the end of the study	Contrast CT	
Every 24 weeks (~8 cycles) thereafter until the end of the study		Contrast CT	PET
30-day follow-up visit ^c		Contrast CT	PET

^a Following complete metabolic response, subsequent scheduled PET assessments are no longer mandatory.

^b Window of \pm 1 week for all timepoints.

^c Tumour assessments will be repeated at this visit for discontinued participants if not previously performed within the required timeframe ie 9 weeks for participants that discontinued before Week 26, and 12 weeks for those that discontinued after Week 26.

If a PET-CT is not available, an independent PET and a diagnostic-quality CT scan (with contrast) can be used. If PET and CT scans are done on the same day, the PET must be performed prior to the contrast-enhanced CT not to compromise the PET read-out.

Post screening, the CT portion of a PET-CT (without contrast) may replace a contrast CT per local institutional practice; however, certain radiographic requirements are needed for acceptance, as described in the Site Radiology Manual, provided separately from this protocol.

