Where contrast CT is contraindicated or unobtainable, MRI or CT (without contrast) with diagnostic quality (sufficient resolution to allow bi-dimensional measurements) may be used instead. In cases where MRI is desirable, the MRI must be obtained at baseline and at all subsequent response evaluations.

Following complete metabolic response, subsequent scheduled PET assessments are no longer mandatory. For participants with baseline hepatosplenomegaly, the cranial-caudal measurement of the spleen and longest diameter of the liver will be assessed at screening and

all subsequent response evaluations.

All response assessments will be made by the investigator. All images for the assessment of response will be collected and stored for central review.

Participants should have radiographic tumour measurements done at the participating study centre or an acceptable alternate imaging facility using an identical imaging protocol and similar equipment. The same imaging equipment should be used for all scans whenever possible. The same radiologist should be assigned to read all the scans for a given participant throughout the study.

Participants who discontinue study intervention for reasons other than PD will continue to be scanned for disease response following the same schedule until documented PD, regardless of the start of new anti-lymphoma treatment.

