5.2.4.2 Derivations

$\text{PFS (months)} = (\text{date of PFS event [progression/death] or censoring} - \text{date of first dose} + 1) / (365.25/12)$.

Participants who have not progressed or died at the time of analysis, or have unknown status, are censored at the time of the latest date of assessment from their last evaluable disease assessment. However, if the participant progresses or dies immediately after 2 or more consecutive missed timepoints, the participant is censored at the time of the latest evaluable disease assessment prior to the 2 missed timepoints. Note: a NE timepoint is not considered as a missed timepoint.

Given the schedule timepoint assessment scheme (ie, 9-weekly for the first 26 weeks then 12-weekly thereafter) the definition of 2 missed timepoints will change.

If the previous assessment is less than study day 113 (ie, week 16) then 2 missing timepoints will equate to 20 weeks since the previous assessment, allowing for early and late timepoints (ie, $2 \times 9 \text{ weeks} + 1 \text{ week for an early assessment} + 1 \text{ week for a late assessment} = 20 \text{ weeks}$).

If the 2 missed timepoints occur over the period when the scheduled frequency of assessment changes from nine-weekly to twelve-weekly this will equate to 23 weeks (ie, take the average of 9 and 12 weeks which gives 10.5 weeks and then apply the same rationale, hence $2 \times 10.5 \text{ weeks} + 1 \text{ week for early assessment} + 1 \text{ week for late assessment} = 23 \text{ weeks}$). The time period for the previous assessment is from study days 113 to 175 (ie, week 16 to week 25).

From week 25 onwards (when the scheduling changes to 12-weekly assessments), 2 missing timepoints equates to 26 weeks (ie, $2 \times 12 \text{ weeks} + 1 \text{ week for an early assessment} + 1 \text{ week for a late assessment} = 26 \text{ weeks}$).

If the participant has no evaluable disease assessments post-baseline or does not have baseline assessment data, they will be censored at Day 1 unless they die within 2 timepoints of baseline (19 weeks plus 1 week allowing for a late assessment within the timepoint window) when the death date qualifies as a PFS event.

A summary of censoring rules and the date of PD/death or censoring are given in [Table 7](#). Note that censoring overrides event in certain specified cases and that this table does not indicate the order for programming.

Table 7 Summary of Censoring Rules for PFS

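### No planned Kaplan-Meier estimate of PFS or DoR counts every documented progression and death, off-treatment disease follow-up is specified two ways, and the rule for participants without evaluable scans has two limits

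*SAP*

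**What the plan says.** **Off-treatment disease follow-up.** Protocol 8.2.2: "Participants who discontinue all study intervention before documented disease progression will be followed according to standard of care until documented disease progression". The Module 1 schedule of activities has a matching row in its long-term follow-up column, "Disease progression follow-up (SoC", which points to 8.2.2. Section 7.1 also refers there, keeping participants in the study "until documented disease progression during the long term follow-up period". On the other side, Section 8 says "All efficacy assessments should continue until progression", including after treatment has stopped. Protocol 10.8.1.2 says that participants who stop for reasons other than progression "will continue to be scanned for disease response following the same schedule until documented PD, regardless of the start of new anti-lymphoma treatment". Section 7.1 itself also tells participants to keep attending visits, with data collected per protocol.

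**Censoring.** Protocol 10.9.4.2.2 defines PFS and DoR to progression or death and describes PFS censoring for participants who have had neither. SAP 5.2.4.1 gives the same PFS definition. SAP 5.2.4.2 then adds "if the participant progresses or dies immediately after 2 or more consecutive missed timepoints, the participant is censored", and Table 7 repeats it. SAP 5.2.3.2 ends DoR on the PFS event or censoring date. SAP Section 3 lists three changes to the protocol analysis (Cycle 1, safety set, survival sweep), and this rule is not among them.

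**No evaluable scan.** For participants with no baseline or no evaluable post-baseline assessment, the text of SAP 5.2.4.2 counts a death within 19 + 1 weeks as an event and otherwise censors at Day 1. Table 7 counts only deaths before the second scheduled post-baseline assessment. In protocol Table 15 that is the row "After 17 weeks (~5 cycles", and SAP Appendix A gives it a window of days 112 to 126.

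**The concern.** A site that follows 8.2.2 can record a genuine progression or death (the eCRF captures both) without the scheduled scans in between. The long-term follow-up visit may even be a telephone call. The SAP would then turn that event into a censored time, often much earlier. Whether an event counts could therefore depend on which protocol section the site obeyed. Both PFS sensitivity analyses (SAP 5.2.4.4) only add censoring, for new therapy and for COVID-19 deaths, and DoR has no sensitivity analysis. This matters most for DoR, which protocol 10.9.2 singles out among the efficacy endpoints that inform success beyond ORR.

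The second problem is a direct contradiction. The SAP text and Table 7 give opposite outcomes for the same death, so two programmers could code it differently.

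**Working it through.** **Day count.** The centres of the SAP Appendix A windows (49–63, 112–126, 175–189) are days 56, 119 and 182, so week w is day 7w. Months are days / 30.4375 (365.25/12).

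**1. The SAP's own limits reproduce.** The SAP gives 2×9+1+1 = 20, 2×10.5+1+1 = 23 and 2×12+1+1 = 26 weeks. From protocol Table 15, the second missed scan minus the last scan, plus one early and one late week, gives (26−8)+2 = 20, (38−17)+2 = 23 and (50−26)+2 = 26. All three match and are not in dispute.

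**2. When the missed-scan rule acts**, with the last evaluable scan at its nominal day and an event censored when it falls more than the limit later:

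| Last scan | Limit | Last day still an event | Censored from |
|---|---|---|---|
| week 8, day 56 | 140 days | 56+140 = 196 | day 197 = 6.5 months |
| week 17, day 119 | 161 days | 119+161 = 280 | day 281 = 9.2 months |
| week 26, day 182 | 182 days | 182+182 = 364 | day 365 = 12.0 months |

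A week-8 scan taken a week early (day 49) moves the first entry to day 190, or 6.2 months.

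**3. Mechanism, on assumed and deliberately extreme dates.** Response at day 56; drug stopped day 77; 30-day visit day 107. Scans at that visit "will be repeated at this visit if they have not been performed within 9 weeks" (for those stopping before week 26). This one is 107−56 = 51 days old, under 63, so it is not repeated. No further evaluable scan is done until progression is documented on day 210.

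- Gap: 210−56 = 154 days, over 140, so the SAP censors.
- PFS: an event at 210/30.4375 = 6.9 months by the protocol definition; censored at 56/30.4375 = 1.8 months by the SAP.
- DoR: an event at 210−56+1 = 155 days (5.1 months) by the protocol definition; censored at 56−56+1 = 1 day by the SAP.

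If ORR were the 25% to 30% quoted for approved drugs in PTCL (an assumption), 21 response-evaluable participants would give 5.25 to 6.3, so 5 or 6 responders. One such case would be 1/6 to 1/5 (17% to 20%) of the DoR sample.

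**4. Frequency and direction.** The documents do not allow either to be computed. A simulation on assumed inputs (21 participants; exponential PFS with median 13 or 26 weeks; 0 to 30% unscanned after week 8; cut at week 52) censored on average 0 to 1.5 events per cohort. At 30% unscanned, the typical median PFS was 12.9 weeks with all events counted against 12.5 under the SAP rule, and 24.2 against 22.0. In an invented 21-participant dataset, censoring two late events cut events from 13 to 11 and moved the median the other way, from 34 to 38 weeks. Among unscanned participants, the rule keeps early events and drops late ones, which can shorten PFS; removing events can lengthen it.

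**5. No-evaluable-scan rule, counted from first dose.**

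- Text: 19+1 = 20 weeks = day 140 (4.6 months).
- Table 7: 8+9 = 17 weeks = day 119 (3.9 months), or day 126 (18 weeks) if the late window is allowed.
- Conflict: days 119–140 (22 days), or 127–140 (14 days). A death there is an event on its own date by the text and a Day 1 censoring by Table 7.
- The 19 does not follow from the 17-week schedule.

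The text, however, counts from baseline, and screening tests may precede first dose by up to 30 days (protocol Table 9, footnote a). From a scan 30 days before first dose, 20 weeks ends near day 140−30 = 110. The conflict would then reverse for deaths from about day 111 to 118. Participants with no baseline scan have no such anchor.

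PFS uses the full analysis set. If that set held 30 (the maximum planned for cHL), one such death would be 1/30 = 3.3% of it.

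**The case against.** The protocol (9.4 and 10.9.4) calls its statistical text a summary and promises a more detailed SAP. A missed-assessment rule can be read as that detail, and SAP 5.2.4.2 says openly that censoring sometimes overrides an event. This stands in part: the rule is deliberate, and its absence from SAP Section 3 is a gap in documentation, not by itself an error. It does not explain why no estimate under the defined endpoint is planned.

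Most protocol text favours continued assessment. Sections 8 and 10.8.1.2 and part of 7.1 point that way, 8.2.2 sits under safety assessments, and 8.1 sends efficacy to the module. A reader might infer that off-treatment participants will go unscanned. The documents do not support that: standard of care does not mean no scans. But the module's own schedule row leads back to 8.2.2, so the conflict remains.

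A reader might also infer that affected cases would be invisible. They would not. All efficacy results are listed (SAP 5.2), swimmer plots show each assessment and when response begins and ends (5.2.1.2 and 5.2.3.3), PFS is broken down by event and censoring type (5.2.4.3), and OS counts deaths regardless. Only the Kaplan-Meier estimates are missing.

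**Conclusion.** The point holds in three parts. The off-treatment follow-up passages conflict. PFS and DoR have no planned Kaplan-Meier estimate with every documented progression and death counted. The SAP text and Table 7 contradict each other for deaths in roughly the two to three weeks up to week 20, if both are counted from first dose.

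The practical size is limited. The missed-scan rule acts from about 6.5 months after a nominal week-8 scan, so it bears more on later analyses than on a six-month primary cut-off, although early enrollees can pass that time before their cohort's cut-off. A claim that PFS or DoR is biased in a particular direction would go too far: the assumed examples move both ways and the number affected is unknown. There is no formal hypothesis, PFS and DoR are secondary and descriptive, and ORR does not depend on this rule.

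**What to change.** (a) State one limit for the no-evaluable-scan rule, derived from the 8+9-week schedule and its window. Name the anchor date, use the same limit in the SAP text and Table 7, and keep its day count consistent with Appendix A.

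(b) Add PFS and DoR sensitivity analyses that count every documented progression and death regardless of missed assessments. Note the missed-scan rule in SAP Section 3 for transparency. The rule itself can stay.

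(c) Reconcile protocol 7.1, 8, 8.2.2, the schedule row and 10.8.1.2 so that a single off-treatment disease-assessment rule applies. Which rule is for the sponsor to decide.

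The cost is text edits to both documents and one extra set of PFS and DoR outputs.

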Situation	Date of PD/Death or Censoring	PFS Outcome
Documented Progressive Disease (PD) or death in the absence of progression	Date of earliest documentation of PD or date of death in the absence of progression	Event
Either no assessment at baseline or no evaluable assessments post-baseline AND death prior to second scheduled post-baseline disease assessment	Date of death	Event
Either no assessment at baseline or no evaluable assessments post-baseline AND no death prior to second scheduled post-baseline disease assessment	Date of first dose (Day 1)	Censored
PD or death (in the absence of progression) immediately after ≥ 2 consecutive missed disease assessments as per the protocol specified assessment schedule	Last evaluable progression-free disease assessment prior to missed assessments	Censored
On-going with neither PD nor death at the time of analysis or lost to follow-up or withdrawn consent	Date of last evaluable disease assessment	Censored
Initiation of subsequent anti-cancer therapy prior to PD or death	Date of last evaluable disease assessment prior to initiation of subsequent anti-cancer therapy	Censored for sensitivity analysis only

Abbreviations: PD, progressive disease; PFS, progression-free survival

The PFS time is always derived based on scan/assessment dates, not timepoint dates.

Disease assessments/scans contributing towards a particular timepoint may be performed on different dates. The following rules are applied:

- The date of progression is determined based on the earliest of the dates of the component that triggered the progression.
- When censoring a participant for PFS the participant is censored at the latest of the dates contributing to a particular overall timepoint assessment.

Note: for target lesions only the latest scan date is recorded out of all scans performed at that assessment for the target lesions and similarly for non-target lesions only the latest scan date is recorded out of all scans performed at that assessment for the non-target lesions.

Duration of follow-up for PFS is applicable only for PFS censored participants and is defined as follows:

Duration of follow-up for PFS in censored participants (months) = (date of PFS censoring – date of first dose + 1) / (365.25/12).

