5.2.4.3 Primary Analysis of Secondary Endpoint: PFS

The main analysis of PFS is based on the FAS. The number and percentage of participants experiencing a PFS event (broken down by type of event/censoring) and Kaplan-Meier plots of PFS will be presented. The median PFS and its 2-sided 80% and 95% CIs will be estimated using the Kaplan-Meier method (if participant numbers allow).

The IP status at progression of participants at the time of analysis will be summarised. This includes the number (%) of participants who were on IP at the time of progression, the number (%) of participants who discontinued IP prior to progression, the number (%) of participants who have not progressed and were on IP or discontinued IP.

A summary of the duration of follow-up for PFS is included using median (range) for censored participants (including all types of PFS censoring).

The proportion of participants alive and progression free at every 3 months (3, 6, 9, 12, etc.) and associated 2-sided 80% and 95% CIs will be estimated using the Kaplan-Meier method.

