5.2.5.2 Derivations

OS (months) = (date of death or censoring – date of first dose + 1) / (365.25/12).

Any participant not known to have died at the time of analysis will be censored based on the last recorded date on which the participant was known to be alive. Participants known to be alive or dead after the DCO for analysis will be censored at the DCO. Participants lost to follow-up will be censored at the date the participant is last known to have been alive. At study closure, any participant still alive after last patient last visit for the study will be censored at the date of last patient last visit.

Note: Survival calls will be made in the week following the date of DCO for the analysis, and if participants are confirmed to be alive or if the death date is after the DCO date these participants will be censored at the date of DCO. The status of ongoing, withdrawn (from the study) and “lost to follow-up” participants at the time of the final OS analysis should be obtained by the site personnel by checking the participant’s notes, hospital records, contacting the participant’s general practitioner and checking publicly-available death registries. In the event that the participant has actively withdrawn consent to the processing of their personal data, the vital status of the participant can be obtained by site personnel from publicly available resources where it is possible to do so under applicable local laws.

Note: For any OS analysis performed in the absence of survival calls being made, it may be necessary to use all relevant eCRF fields to determine the last recorded date on which the participant was known to be alive for those participants still on intervention (since the SURVIVE module is only completed for participants off IP if a survival sweep is not performed). The last date for each individual participant is defined as the latest among the following dates recorded on the eCRFs:

- AE start, stop and change in severity dates
- Admission and discharge dates of hospitalization
- Study IP date
- End of IP date
- Concomitant medication start and stop dates
- Laboratory test dates
- Date of vital signs
- Disease assessment dates on eCRF
- Start and stop dates of alternative anticancer intervention
- Date last known alive on survival status eCRF
- End of study date

Duration of follow-up for OS is reported separately for censored participants and non-censored participants as well as combined for all participants and is defined as follows:

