Duration of follow-up for OS (months) = (date of death or censoring [date last known to be alive]) – date of first dose + 1) / (365.25/12).

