5.2.5.4 Primary Analysis of Secondary Endpoint (Overall Survival)

The analysis of OS is based on the FAS. The number and percentage of participants experiencing an OS event and Kaplan-Meier plots of OS will be presented. The median OS and 2-sided 80% and 95% CIs will be estimated using the Kaplan-Meier method (if participant numbers allow).

Summaries of the number and percentage of participants who have died, those still in survival follow-up, those lost to follow-up and those who have withdrawn consent will be provided.

A summary of the duration of follow-up for OS will be included using median (range). This is presented separately for censored and non-censored participants.

The proportion of participants alive at every 3 months (3, 6, 9, 12, etc.) and associated 2-sided 80% and 95% CIs will be estimated using the Kaplan-Meier method.

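### PFS follow-up is summarised only in censored participants, so it depends on the event rate and understates how long the cohort was observed; the two OS sections also disagree

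*SAP*

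**What the plan says.** **PFS.** SAP 5.2.4.2: "Duration of follow-up for PFS is applicable only for PFS censored participants and is defined as follows"; the formula runs from first dose to the censoring date. SAP 5.2.4.3: "A summary of the duration of follow-up for PFS is included using median (range) for censored participants", with every type of PFS censoring included. No other PFS follow-up summary is planned.

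**Censoring dates.** Under 5.2.4.2, participants without an event "are censored at the time of the latest date of assessment from their last evaluable disease assessment". Those with no baseline data or no evaluable post-baseline assessment are treated differently: "they will be censored at Day 1 unless they die within 2 timepoints of baseline".

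**OS.** SAP 5.2.5.2: "Duration of follow-up for OS is reported separately for censored participants and non-censored participants as well as combined for all participants", with death as the end date for those who died. SAP 5.2.5.4, on what will be shown: "This is presented separately for censored and non-censored participants". The combined row is not mentioned there.

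**DoR.** SAP 5.2.3 defines no follow-up measure, although protocol 10.9.2 singles out DoR among the other efficacy endpoints that count towards success.

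**The concern.** Median follow-up tells a reader whether DoR, PFS and OS are mature. It should describe how long the cohort was watched, whatever happened to its members. Removing everyone who progressed or died leaves a group weighted towards recent entrants, together with anyone censored at Day 1. Two cohorts watched equally long but with different event rates would then report different follow-up. The study presents three diseases side by side, so this is likely to occur.

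For OS, ending follow-up at death turns the figure for those who died into time to death, and pulls down any figure that includes them.

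**Working it through.** The documents state no follow-up target, so there is no planned figure to reproduce.

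**Inputs from the documents**
- 21 response-evaluable participants per cohort (SAP 4.2.3.7).
- The primary cut-off comes at 6 months' opportunity for follow-up (or earlier progression or new therapy), or when 75% have progressed or died, whichever is first (SAP 4.2.1).
- Scans fall at weeks 8, 17 and 26, then every 12 weeks (protocol Table 15).

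**Assumptions, because the documents give none.** Uniform accrual over 12 or 24 months; exponential PFS with median 2, 4 or 8 months; exponential OS with median 10 months, drawn independently; no Day 1 censoring unless stated. The 75% is applied to 21 participants, although the full analysis set may be somewhat larger.

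**Step 1: size of the group.** 0.75 × 21 = 15.75, so 16 events are needed and 21 − 16 = 5 remain censored.

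**Step 2: weight of a Day 1 censoring.** (0 + 1) / (365.25/12) = 0.03 months.

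**Step 3: dependence on event rate alone.** Fix the cut at 6 months after the last first dose, with 12-month accrual. True median potential follow-up (first dose to cut-off) is then 11.5 months whatever the PFS. The censored-only median is 8.2, 9.2 and 10.1 months at median PFS 2, 4 and 8 months. The observation is the same, yet three different figures result.

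**Step 4: the trial's own cut-off rule.** The cut is at the 16th event (or full enrolment if later), or at 6 months after the last first dose if that is sooner. Accrual is 12 months and event times are exact.

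| Median PFS (months) | True follow-up | Censored-only | Reverse Kaplan-Meier, where estimable | Reverse Kaplan-Meier median not reached |
|---|---|---|---|---|
| 2 | 6.0 | 2.0 | 5.6 | 28% |
| 4 | 8.6 | 6.2 | 9.1 | 4% |

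These are simulated values. A separate run, averaged over cohorts, gave 2.2 against 6.0 and 6.2 against 8.7. With 24-month accrual that run gave 1.5 against 10.9 and 4.5 against 12.0.

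**Step 5: the SAP's censoring dates.** With 12-month accrual, median PFS 4 months and the 75% trigger, using scan dates gives 6.2 against 9.7. Adding 10% Day 1 censoring gives 4.5 against 9.8.

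**Step 6: OS.** In the 12-month, median PFS 4 months setting with the trigger and exact times, OS follow-up is 7.6 months in censored participants, 3.8 in those who died and 5.8 combined. The true figure is 8.7; reverse Kaplan-Meier gives 8.8.

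**The case against.** The strongest reply is that this is one descriptive row, openly labelled as covering censored participants, in a single-arm study with no formal hypotheses. The SAP also gives event and censoring counts by type, three-monthly Kaplan-Meier estimates with intervals, swimmer plots and counts still on study. All of that stands, and it limits the importance of the point. It does not say how long each cohort was observed.

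Four stronger readings are tempting, but the documents do not support them.

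- **OS follow-up is reported only by vital status.** SAP 5.2.5.2 expressly adds a combined figure. What remains is that 5.2.5.4 omits it and that follow-up ends at death.
- **The PFS row will often be empty.** With median PFS 2 months, 33% to 64% of simulated cohorts had nobody censored, but only when the 6-month rule alone set the cut. Under the whichever-first rule in SAP 4.2.1 the share was 0%. An empty row could still arise at a later cut, such as the final analysis.
- **Reverse Kaplan-Meier removes the problem.** It removes selection on outcome if censoring is independent. It keeps the Day 1, last-scan and missed-visit censoring, and its median may not be estimable: not reached in 4% to 28% of cohorts in the table above, and in up to about 87% of cohorts in the most extreme scenario run.
- **The efficacy results are biased.** The follow-up row does not enter ORR, CR rate or any Kaplan-Meier estimate.

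**Conclusion.** The point holds as a minor reporting weakness. The planned PFS follow-up depends on outcome, rests on about 5 of 21 participants if the 75% trigger sets the cut-off, and fell below true potential follow-up in every scenario run. Under 12-month accrual with the trigger and exact times, the shortfall is about 4.0 months at median PFS 2 months (6.0 − 2.0) and 2.4 months at median PFS 4 months (8.6 − 6.2). The sizes rest on the assumed accrual and event rates; the direction did not change across those tried. For OS, 5.2.5.2 and 5.2.5.4 need reconciling, and the combined figure is also too low because it stops at death.

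**What to change.** In SAP 5.2.4.3 and 5.2.5.4, report median follow-up for PFS and OS in the full analysis set by reverse Kaplan-Meier (events treated as censored, censorings as events). In 5.2.3.3, do the same for DoR in responders, measured from first response.

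Alongside these, give the median and range of time from first dose to data cut-off for all participants in the full analysis set. This is always estimable and covers cohorts where the reverse Kaplan-Meier median is not reached. Keep the censored-only PFS row as secondary. Add the combined OS row to 5.2.5.4 so that it matches 5.2.5.2, noting that it ends at death.

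The cost is a few SAP sentences and a little programming, with no new data. The downside is an occasional reverse Kaplan-Meier entry marked as not reached, and a footnote that Day 1 and last-scan censoring still affect it.
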